1. INTRODUCTION

This is the Statistical Analysis Plan (SAP) for the “DURATION” trial, a multicenter, non-inferiority, open labelled, pragmatic randomized clinical trial comparing different durations of antibiotic therapy in infection of osteosynthesis material (IOM) implanted after long bone fractures and treated with debridement and material retention.

This SAP was developed before the initiation of the study.

1.1 Study hypothesis

The hypothesis of the study is that in IOM of long bone fracture, a short antibiotic treatment is equally effective as a long antibiotic treatment in patients selected for debridement and implant retention. Antibiotic duration can be selected according to the time of diagnosis of IOM as it takes into account the biofilm formation and the state of fracture consolidation:

- a) In patients with early infections (those that occur in the first 2 weeks after implantation of the osteosynthesis material) in whom early debridement is performed, it is possible to shorten the duration of antibiotic treatment to 8 weeks (versus 12 weeks);
- b) In patients with delayed infections (those that occur between 3 and 10 weeks after implantation of the osteosynthesis material) in whom it is not possible to remove the implant due to instability/lack of fracture healing, it is possible, after surgical debridement, to shorten the duration of antibiotic treatment to 12 weeks (vs. maintaining antibiotic treatment until fracture healing or implant removal).
- c) In patients with late infections (those that occur more than 10 weeks after implantation of the osteosynthesis material) healing is not possible until the implant is removed, but when removal is not possible, antibiotic therapy can be maintained until fracture healing or implant removal.

1.2 Primary Study Objective

To evaluate whether, after performing surgical debridement in patients with IOM due to a large bone fracture, a short antibiotic treatment is as effective as a longer treatment.

1.3 Secondary Study Objectives

- To evaluate the efficacy and safety of different antimicrobials used in IOM
- To evaluate the development of antimicrobial resistance during antibiotic treatment
- To evaluate the need for new surgeries during follow-up
- To provide information about the functional prognosis and quality of life of the patient according to each of the treatment strategies
- To evaluate the consumption of health resources with each type of strategy
- To evaluate the different reconstruction strategies (bone and soft tissue) carried out in order to recover lost functionality (degree of mobility and autonomy).

1.4 Primary endpoint

The primary endpoint is the variable "cure" composed by all of the following: a) clinical cure in the test of cure (TOC) (see definition below); b) radiological healing; c) definitive soft tissue coverage at TOC.

The definitions for all the outcomes are specified in the study protocol. The TOC will be performed 12 months after the end of antibiotic therapy prescribed to treat IOM following DAIR, except in patients with delayed infections randomized to the long-treatment regimen (until fracture union) who receive 6 months or more of antibiotic treatment, which will be evaluated 18 months after the start of the study (or randomization).

1.5 Secondary endpoints

- a) **Clinical endpoints:** efficacy of each group of antibiotics, secondary infections, infection recurrence rate (relapses and reinfections), need for new surgeries (debridement, material removal, covering, amputation), reconstructive surgery strategies (bone and soft tissue), functional status (defined as restoration of limb function prior to fracture) and state of health.
- b) **Microbiological endpoints:** Resistance development to antibiotic used during therapy and *C. difficile* infection during therapy and at 30-day.
- c) **Adverse events (AE) and complications:** Adverse events and severity, including death (that is, all-cause mortality).
- d) **Consumption of health resources:** Consumption of health resources will be evaluated for each type of strategy: days of antibiotic treatment, length of hospital stay, readmissions, number and type of surgeries performed.

1.6 Interim Analyses

Interim analysis will be conducted when 75 patients have been included to assess the frequency of the event rate and inclusion rate to adjust the intended size of the study population.

2. STUDY POPULATIONS

The populations for analysis will be:

2.1 Intent-to-treat (ITT) population (ITT): all appropriately-included and randomized patients.

2.2 Per protocol population (PP): all patients who received the complete antibiotic treatment regimen according to the inclusion group.

2.4 Clinically evaluable population (CEP): all patients with evaluation of success at the test of cure at 12 months after completion of treatment, or who have clinical failure before TOC.

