4.2 Missing Data

Missing data for key study variables, if any, will be presented and compared across study arms. Missing data for secondary exposure or variables will be considered as such and presented. No imputation of missing data is planned.

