5. STATISTICAL ANALYSIS

5.1 Primary endpoint

The primary endpoint will be collected as a dichotomous variable (yes/no). The primary analysis will be the absolute difference in the proportion of patients reaching the composited primary outcome variable “cure” in the study arms (with one-sided 95% confidence interval) in the ITT population, with the long antibiotic treatment as the reference group. The specific reasons for not reaching overall success (failure, withdrawals, death, etc.) will be specified in both study arms.

A secondary analyses will include subgroups analysis for the primary outcome using the same procedure, and the comparison of the composite variable components (clinical cure, radiological healing and soft tissue coverage) in the PP and CEP, after excluding incorrectly assigned patients.

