5.2 Secondary endpoints

The secondary endpoints will be collected as dichotomous variables (yes/no) or continuous variables. The ITT, PP and CEP approaches will be used for the analyses of secondary endpoints. The absolute difference with one-side 95% CI proportion will be used for dichotomous variables and absolute difference with one-side 95% CI mean/median (as appropriate) for continuous variables.

5.2.1 Clinical endpoints:

Efficacy of each group of antibiotics used, secondary infections, infection recurrence rate (relapses and reinfections), need for new surgeries (debridement, material removal, covering, amputation), reconstructive surgery strategies (bone

and soft tissue), and functionality of the lower limbs will be reported as proportion. Risk ratios (RRs) and the absolute difference for achieving each endpoint (with 95% CIs), with the long antibiotic treatment arm as the reference group, will be calculated.

Functionality of the upper limbs (Quick-DASH score) and health outcomes (SF-12 or Barthel scores) will be reported as median. The median of each score will be compared between the two treatment groups using parametric or nonparametric tests as appropriate.

5.2.2 Microbiological endpoints: Resistance development to antibiotic used during therapy and *C. difficile* infection during therapy and at 30-day will be reported as proportion. Risk ratios (RRs) and the absolute difference for achieving each endpoint (with 95% CIs), with the long antibiotic treatment arm as the reference group, will be calculated.

5.2.3 Adverse events (AE) and complications: Adverse events and severity, including death (that is, all-cause mortality) will be reported as proportion. Risk ratios (RRs) and the absolute difference for achieving each endpoint (with 95% CIs), with the long antibiotic treatment arm as the reference group, will be calculated.

5.2.4 Consumption of health resources will be evaluated for each type of strategy: days of antibiotic treatment, length of hospital stay, readmissions, and number of surgeries performed will be reported as median. The median of each variable will be compared between the two treatment groups using parametric or nonparametric tests as appropriate.

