5.3 Subgroup analyses

The primary and secondary endpoint will be analysed in the following subgroups:

- Type of infection: early and delayed.
- Type of fracture: open (Gustilo and Anderson classification) or closed.
- Type of osteosynthesis material: endomedullary nail or needle, plates or screws.
- According to the etiology of the infection: infections by different microorganisms, infections by multidrug-resistant microorganisms.

- According to type of patient: comorbidities, elderly, renal insufficiency, gender.

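### The CEP definition omits the 18-month exception to the test of cure, so read literally it excludes on outcome in the long arm only; overall cure is clearly planned only in the ITT

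*SAP*

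**What the plan says.** Section 1.4 sets the test of cure (TOC) at 12 months after the end of antibiotics, with one exception. It covers delayed infections randomised to the long regimen "who receive 6 months or more of antibiotic treatment, which will be evaluated 18 months after the start of the study (or randomization"). Section 1.1 leaves the length of that regimen open: "maintaining antibiotic treatment until fracture healing or implant removal".

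Section 2.4 defines the CEP with a single fixed time and no exception: evaluation of success "at the test of cure at 12 months after completion of treatment, or who have clinical failure before TOC".

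The CEP is used in three places. Section 5.1 plans the "comparison of the composite variable components (clinical cure, radiological healing and soft tissue coverage) in the PP and CEP". Section 5.2 states: "The ITT, PP and CEP approaches will be used for the analyses of secondary endpoints". Section 5.3 repeats the primary and secondary endpoints by subgroup, the first being "Type of infection: early and delayed". The difference in overall cure, with its one-sided 95% confidence interval, is placed in the ITT population (section 5.1).

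**The concern.** The two sections give different times for the same visit in one group of patients, and that group exists in one arm only. If section 2.4 is applied as written, a long-arm delayed patient treated for more than six months who attends the scheduled TOC and is cured does not qualify for the CEP, because the visit was not 12 months after completion. The same patient with a clinical failure before the TOC does qualify. That is an exclusion that depends on outcome and operates in the reference arm alone. It would enter every CEP comparison of the components and secondary endpoints, and weigh most in the delayed subgroup, where these patients form a larger share of the long arm.

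A second, smaller matter is that the SAP does not plainly say whether overall cure will be compared outside the ITT. In a non-inferiority trial a reader will want that comparison in the PP and CEP, and should not have to infer it from sentence structure.

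**Working it through.** The SAP extract states no margin, arm size, cure rate or loss rate, so there is no planned figure to reproduce. Step 1 uses the document's own figures. Steps 2 to 4 are illustrations on assumed values.

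**1. Timing.** Let T be months of antibiotics, counted from study start or randomisation. The section 1.4 exception puts the TOC at 18 − T months after completion; section 2.4 asks for 12.

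| T (months) | TOC after completion, section 1.4 | Section 2.4 |
|---|---|---|
| 6 | 12 | 12 |
| 7 | 11 | 12 |
| 9 | 9 | 12 |
| 12 | 6 | 12 |

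The two agree at exactly six months and differ for every longer course. If antibiotics begin before randomisation and the 18 months run from randomisation, the point of agreement shifts accordingly. The short regimens are 8 and 12 weeks (section 1.1) and the exception names only the long arm, so no short-arm patient is affected.

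**2. Effect on long-arm cure in a literal CEP.** Assume no loss to follow-up. Let f be the share of the long arm that is delayed and treated over six months, pX their true cure, pR the true cure in the rest, and c the share of their non-cures that are clinical failures before the TOC. Then

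CEP cure = pR(1 − f) / [(1 − f) + f(1 − pX)c].

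With pR = pX = 0.80:

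| f | c = 1 | c = 0.5 |
|---|---|---|
| 10% | 78.3% | 79.1% |
| 20% | 0.64/0.84 = 76.2% | 0.64/0.82 = 78.0% |
| 30% | 73.7% | 76.7% |
| 40% (as might hold within the delayed subgroup) | 70.6% | 75.0% |

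In patients, at f = 20% and c = 1: of 100 in the long arm, 20 are treated over six months, 16 cured and 4 failed. The CEP drops the 16 and keeps the 4, leaving 64 cured of 84. With truly equal arms, f = 20% gives a spurious 3.8 (c = 1) or 2.0 (c = 0.5) points in favour of the short arm. A true 70% against 80% reads −6.2 or −8.0 instead of −10.

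**3. Where the direction turns.** Let p be overall long-arm cure. CEP cure equals p when c = (p − pX) / [p(1 − pX)], whatever f is. With p = 0.80:

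- pX = 0.70 gives 0.10/(0.80 × 0.30) = 41.7%.
- pX = 0.60 gives 0.20/(0.80 × 0.40) = 62.5%.

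Below these values long-arm cure is overstated. Example: f = 20% and pX = 0.60 imply pR = (0.80 − 0.12)/0.80 = 0.85. With c = 0.3, CEP cure = 0.68/(0.80 + 0.024) = 82.5%, which works against the short arm.

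**4. A quantity that clearly is planned in the CEP.** Take clinical failure, with a true long-arm rate of 10% in all patients and every failure recorded before the TOC. At f = 20% the literal CEP gives 0.10/(0.80 + 0.20 × 0.10) = 0.10/0.82 = 12.2%.

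**5. Overall cure outside the ITT.** In section 5.1 the words naming the PP and CEP attach to the three components. Section 5.2 covers secondary endpoints only. No sentence plainly plans the overall cure difference in either set.

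**The case against.** The strongest reply is that section 2.4 uses a term already defined in section 1.4, exception included, and repeats only its general rule. On that view nobody would discard a patient who attended the scheduled visit and was cured, and section 3 has assignment to populations settled before database lock by assessors blinded to outcomes. This is probably the intent. It does not remove the conflict: section 2.4 states a fixed time where it could have pointed to section 1.4. Blinded assessors need one rule, and blinding does not help if the rule itself depends on failure.

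It is also fair to say that most of the illustration concerns overall cure in the CEP, an analysis the SAP does not clearly plan. Step 4 shows that a planned component is affected too. Every secondary endpoint is also analysed in the ITT and PP, which this wording leaves alone.

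The closing words of the section 5.1 sentence could be stretched to cover the primary outcome as well as its components. That is why the second point is put no higher than not clearly planned.

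A reader might infer that the literal rule always favours non-inferiority. It does not. Treatment continues until healing or implant removal, so courses over six months may select slow healers. Cure also requires radiological healing and soft tissue coverage, so many of their non-cures need not be clinical failures. Step 3 shows that the sign can then reverse.

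**Conclusion.** The CEP definition and the TOC schedule conflict and must be reconciled. As written, long-arm delayed patients treated for more than six months enter the CEP only through clinical failure. If they cure as often as the rest, the illustration at 80% cure and f = 20% understates long-arm cure by 2.0 to 3.8 points. The actual size and sign cannot be derived from the SAP: the cure rate, f and c are all assumed.

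Three stronger readings are not supported:

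- The primary result is not compromised; it is an ITT analysis and does not use the CEP.
- The CEP cannot be called the plan's failed safeguard against loss to follow-up, because the SAP gives it no such role.
- The treatment of missing outcomes is not shown to be an error. Section 5.1 says "The specific reasons for not reaching overall success (failure, withdrawals, death, etc.) will be specified in both study arms", which largely implies that patients who withdraw count as not cured. Section 4.2 adds: "Missing data for key study variables, if any, will be presented and compared across study arms". An explicit rule for patients with no TOC status would be clearer, but a further sensitivity analysis is an optional addition.

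The lack of a clear plan for overall cure in the PP and CEP stands as a separate, modest gap. The point should be fixed, mainly because the correction is so cheap.

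**What to change.** 1. In section 2.4, define the CEP as patients evaluated at the TOC as scheduled in section 1.4, including its 18-month exception, or with clinical failure before that TOC. Long-arm patients treated over six months then enter whether cured or failed, and the artificial difference in the illustration becomes zero. No visit or treatment changes.
2. In section 5.1, state that the overall cure difference with its one-sided 95% confidence interval is also reported in the PP and CEP as supporting analyses.
3. Optional: confirm in sections 4.2 and 5.1 that ITT patients with no TOC status count as not cured, and add a sensitivity table that varies this scoring. For scale, with an assumed true 70% against 80% and equal loss w in both arms, that scoring gives −10 × (1 − w) points: −9 at 10% loss and −8 at 20%. With equal cure and equal loss the shift is zero.

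The cost is SAP wording and a little programming, with no new data. If the optional table includes a worst-case corner, it will look unfavourable and should be read as a bound.

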3. ASSIGNMENT TO POPULATIONS AND PROTOCOL VIOLATIONS

To avoid a possible bias due to the open nature of the trial, the evaluation of the results will be double-check by an independent committee blinded (not part of the study as investigators) with respect to the assignment of treatment. This committee will be made up of 3 expert researchers who are not participating as researchers in this study and who will reach their conclusions by consensus after reviewing the consistency of outcome data as included in the CRF by local investigators, once these data has been verified by the monitoring team according to source data. All protocol violations occurring after randomisation will be collected. The final assignment of participants to the ITT, PP and CEP will be made after reviewing the protocol violations prior to database lock, with assessors blinded to the outcomes.

4. DATABASE AND MISSING DATA

4.1 Database archive and validation

The study database will be exported from the electronic CRF to SPSS software, and will be maintained at FISEVI files. The Spanish Clinical Research Network (SCReN) team will monitor the data for coherence, missing values and outliers, according to their standard monitoring procedures. All corrections will be performed by the study team together with the external monitoring team before database lock.

4.2 Missing Data

Missing data for key study variables, if any, will be presented and compared across study arms. Missing data for secondary exposure or variables will be considered as such and presented. No imputation of missing data is planned.

5. STATISTICAL ANALYSIS

5.1 Primary endpoint

The primary endpoint will be collected as a dichotomous variable (yes/no). The primary analysis will be the absolute difference in the proportion of patients reaching the composited primary outcome variable “cure” in the study arms (with one-sided 95% confidence interval) in the ITT population, with the long antibiotic treatment as the reference group. The specific reasons for not reaching overall success (failure, withdrawals, death, etc.) will be specified in both study arms.

A secondary analyses will include subgroups analysis for the primary outcome using the same procedure, and the comparison of the composite variable components (clinical cure, radiological healing and soft tissue coverage) in the PP and CEP, after excluding incorrectly assigned patients.

5.2 Secondary endpoints

The secondary endpoints will be collected as dichotomous variables (yes/no) or continuous variables. The ITT, PP and CEP approaches will be used for the analyses of secondary endpoints. The absolute difference with one-side 95% CI proportion will be used for dichotomous variables and absolute difference with one-side 95% CI mean/median (as appropriate) for continuous variables.

5.2.1 Clinical endpoints:

Efficacy of each group of antibiotics used, secondary infections, infection recurrence rate (relapses and reinfections), need for new surgeries (debridement, material removal, covering, amputation), reconstructive surgery strategies (bone

and soft tissue), and functionality of the lower limbs will be reported as proportion. Risk ratios (RRs) and the absolute difference for achieving each endpoint (with 95% CIs), with the long antibiotic treatment arm as the reference group, will be calculated.

Functionality of the upper limbs (Quick-DASH score) and health outcomes (SF-12 or Barthel scores) will be reported as median. The median of each score will be compared between the two treatment groups using parametric or nonparametric tests as appropriate.

5.2.2 Microbiological endpoints: Resistance development to antibiotic used during therapy and *C. difficile* infection during therapy and at 30-day will be reported as proportion. Risk ratios (RRs) and the absolute difference for achieving each endpoint (with 95% CIs), with the long antibiotic treatment arm as the reference group, will be calculated.

5.2.3 Adverse events (AE) and complications: Adverse events and severity, including death (that is, all-cause mortality) will be reported as proportion. Risk ratios (RRs) and the absolute difference for achieving each endpoint (with 95% CIs), with the long antibiotic treatment arm as the reference group, will be calculated.

5.2.4 Consumption of health resources will be evaluated for each type of strategy: days of antibiotic treatment, length of hospital stay, readmissions, and number of surgeries performed will be reported as median. The median of each variable will be compared between the two treatment groups using parametric or nonparametric tests as appropriate.

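### SAP 5.2 sets one-sided 95% CIs, with no direction, for all secondary differences, while 5.2.1 to 5.2.3 set plain 95% CIs for the same differences

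*SAP*

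**What the plan says.** Section 5.1 analyses cure as an absolute difference in proportions, "with one-sided 95% confidence interval) in the ITT population, with the long antibiotic treatment as the reference group". A one-sided interval fits there, because the trial is a non-inferiority trial and cure is its primary endpoint.

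Section 5.2 opens by extending one-sided intervals to the secondary endpoints: "The absolute difference with one-side 95% CI proportion will be used for dichotomous variables and absolute difference with one-side 95% CI mean/median".

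The subsections on yes/no endpoints (5.2.1 clinical, 5.2.2 microbiological, 5.2.3 adverse events) each set a different-looking rule: "Risk ratios (RRs) and the absolute difference for achieving each endpoint (with 95% CIs), with the long antibiotic treatment arm as the reference group". None of the three mentions one-sidedness. Section 5.2.3 covers the harms: "Adverse events and severity, including death (that is, all-cause mortality) will be reported as proportion".

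For continuous outcomes, 5.2.1 and 5.2.4 specify between-group tests and do not mention intervals. In 5.2.4 the wording is: "The median of each variable will be compared between the two treatment groups using parametric or nonparametric tests as appropriate".

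**The concern.** One estimate, the absolute difference with the long arm as reference, has two interval rules within one section. An analyst could follow either and be within the plan. The trial is open-label, so the choice should be settled before results are seen.

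The one-sided rule is also incomplete. For cure, where higher is better, the informative limit on short minus long is the lower one. For adverse events, death, resistance, C. difficile and recurrence, higher is worse, so the sides reverse. For reconstructive strategies no worse direction is defined. The SAP fixes no side for any of these, and it gives no secondary margin or hypothesis from which a side could be inferred.

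At stake is whether the safety results can show an effect in either direction, and at what error rate.

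**Working it through.** **Inputs.** The confidence levels come from SAP 5.2 and 5.2.1 to 5.2.3. The SAP gives no event rates or arm sizes and no secondary margin, so there is no figure of its own to reproduce. The rates and arm sizes below are assumptions, used only to show what each rule would report.

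**Step 1: critical values.**
- One-sided 95%: z = 1.645, error 5% on the reported side. This is the same limit as in a two-sided 90% interval.
- Two-sided 95%: z = 1.960, error 2.5% per side.
- Ratio: 1.960 / 1.645 = 1.19. Each two-sided limit lies 19% further from the estimate. Seen the other way, 1.645 / 1.960 = 0.84, so the one-sided limit is 16% closer.

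**Step 2: Wald limits for an adverse event difference.** d = p_short − p_long; SE = √[p_short(1 − p_short)/n + p_long(1 − p_long)/n]; limits d ± z × SE.

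Worked example, 10% short against 20% long, 75 per arm: SE = √[(0.09 + 0.16)/75] = 0.0577. One-sided upper bound: −0.100 + 1.645 × 0.0577 = −0.005. Two-sided: −0.100 ± 1.960 × 0.0577 = −0.213 to +0.013.

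Results in percentage points:

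| Short vs long | n per arm | One-sided upper only | One-sided lower only | Two-sided 95% |
|---|---|---|---|---|
| 10% vs 20% | 75 | −0.5 | −19.5 | −21.3 to +1.3 |
| 10% vs 20% | 100 | −1.8 | −18.2 | −19.8 to −0.2 |
| 10% vs 20% | 150 | −3.3 | −16.7 | −18.0 to −2.0 |
| 30% vs 20% | 75 | +21.6 | −1.6 | −3.8 to +23.8 |
| 30% vs 20% | 150 | +18.2 | +1.8 | +0.3 to +19.7 |
| 30% vs 20% | 200 | +17.1 | +2.9 | +1.6 to +18.4 |

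**Step 3: reading the table.**
- *Level.* At 75 per arm and 10% against 20%, the one-sided upper bound excludes zero and the two-sided interval does not. At 100 and 150 per arm both exclude it. The change of level alone matters only near the boundary.
- *Direction, upper bound only.* At 30% against 20% and 150 per arm, +18.2 does not show that the short arm has more events. The two-sided lower limit of +0.3 does.
- *Direction, lower bound only* (the side suited to cure, carried over to harms). At 10% against 20% and 150 per arm, −16.7 does not show that the short arm has fewer events. The two-sided upper limit of −2.0 does.

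The missing direction is the larger problem, because no sample size removes it.

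**The case against.** The subsections never say two-sided. Their plain 95% CIs could be shorthand for the general rule, or specific text meant to override it. Neither reading can be excluded. Against shorthand, the SAP names one-sidedness in 5.1 and at the start of 5.2 but omits it in all three subsections. Those subsections also apply the same 95% CIs to risk ratios, for which no one-sided rule is given. Even if shorthand is accepted, the bound still has no stated side.

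If the subsection intervals are two-sided, the risk ratio intervals would already show an effect in either direction, whatever is done with the difference. That stands and limits the damage for yes/no endpoints. It does not settle the interval for the absolute difference, which is the measure named in both rules.

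A reader might infer that a one-sided bound cannot show that shorter therapy is safer. That goes too far. An upper bound on short minus long can fall below zero, as the −0.5 above does, and it does so more readily than a two-sided limit. Only a lower bound would miss a benefit.

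A reader might also assume that the trial expects a safety gain. The SAP does not say so. Its hypothesis is that "a short antibiotic treatment is equally effective as a long antibiotic treatment in patients selected for debridement and implant retention", and its safety objective is "To evaluate the efficacy and safety of different antimicrobials used in IOM".

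Nor do the tests in 5.2.4 contradict 5.2, since a test and an interval for the same difference can be reported together.

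Finally, one-sided intervals may be defended for efficacy-type secondary outcomes such as recurrence or function in a non-inferiority trial. That is fair, provided that the side and the margin are stated. The SAP states neither.

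**Conclusion.** The point holds as a conflict over sidedness together with a one-sided rule that has no direction. The level conflict depends on reading an unqualified 95% CI as two-sided, which is the convention. The missing direction does not depend on that reading.

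The two rules put the limits 19% apart in distance from the estimate and double the per-side error (5% against 2.5%). For adverse events, death, resistance and C. difficile, a single bound leaves either harm or benefit of the short regimen unassessed. The worked intervals rest on assumed rates of 10% to 30% and 75 to 200 per arm. They illustrate the mechanism and do not predict this trial's results.

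The primary non-inferiority conclusion is untouched. The plan should be corrected because it does not determine how its safety differences are reported.

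**What to change.** Replace the interval rule at the start of 5.2 with one sentence along these lines: all secondary and safety endpoints, dichotomous and continuous, will be reported with two-sided 95% confidence intervals; the one-sided 95% interval is used only for the primary non-inferiority comparison. Add the word two-sided to the intervals in 5.2.1, 5.2.2 and 5.2.3 so that the risk ratios and differences match.

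If a one-sided interval is wanted for a particular efficacy outcome, name that endpoint and state the side and the margin.

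The cost is one sentence and three one-word edits, with no new data. Secondary limits will lie about 19% further from the estimate than under the one-sided rule, so some borderline differences will no longer exclude zero, as in the 75-per-arm example.

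### SAP 5.2.4 reports readmissions and number of surgeries as medians, which can be 0 in both arms even when one arm has twice the events

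*SAP*

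**What the plan says.** Resource use is a secondary objective (SAP 1.3). SAP 1.5 lists its components as "days of antibiotic treatment, length of hospital stay, readmissions, number and type of surgeries performed".

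The opening of SAP 5.2 recognises two kinds of variable: "The secondary endpoints will be collected as dichotomous variables (yes/no) or continuous variables". For the second kind it foresees an "absolute difference with one-side 95% CI mean/median (as appropriate) for continuous variables". Counts are not named as a type of their own.

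SAP 5.2.4 then settles the choice for resource use. It states that "readmissions, and number of surgeries performed will be reported as median" (days of antibiotics and length of stay are in the same list), and continues: "The median of each variable will be compared between the two treatment groups using parametric or nonparametric tests as appropriate".

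SAP 5.2.1 separately covers "need for new surgeries (debridement, material removal, covering, amputation), reconstructive surgery strategies" and other clinical endpoints. These are reported as proportions, with risk ratios and absolute differences and 95% CIs. There is no corresponding line for readmissions.

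**The concern.** A median says where the middle patient lies. For a count in which most patients have none, the middle patient has none, whatever happens to the rest. The difference in medians is then 0 and its interval is close to uninformative.

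Resource use depends on the total, which is the mean times the number of patients. The median does not recover it. An excess or a saving in readmissions could therefore be present in the data and absent from the effect estimate that the plan asks for. The possible gain from shorter treatment is part of what this secondary objective is meant to describe.

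**Working it through.** **Inputs.** The SAP gives the summary (median) and the comparison (medians, test left open). It gives no readmission or surgery rate, no dispersion and no sample size, so there is no figure of its own to reproduce. Everything numerical below is an assumption, shown over a range: Poisson or negative binomial counts, with one arm at mean m and the other at 2m. The arm sizes of 75 and 150 are also assumed; the 75 patients in SAP 1.6 are the total at the interim analysis.

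**Step 1: when is the median 0?** It is 0 when P(no event) exceeds 0.5.

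- Poisson: P(0) = exp(−m), so m < ln 2 = 0.693.
- Negative binomial with dispersion k: P(0) = (k/(k+m))^k. For k = 1, 1/(1+m) > 0.5 gives m < 1.0. For k = 0.5, 0.5/(0.5+m) > 0.25 gives m < 1.5.

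Both medians are 0 if the arm with the higher rate lies below these limits.

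**Step 2: a doubling that the medians miss.** Poisson 0.30 v 0.60:

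- P(at least one) = 1 − exp(−0.30) = 0.26, and 1 − exp(−0.60) = 0.45.
- Medians: 0 v 0.
- Expected totals at 150 per arm: 150 × 0.30 = 45 v 150 × 0.60 = 90 events.

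**Step 3: doublings over a range.** Population medians, and the share of 2000 simulated trials in which the two sample medians were equal:

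| Means | Poisson medians | Equal, 75 per arm | Equal, 150 per arm | Neg. bin. (k = 1) medians | Equal, 75 per arm | Equal, 150 per arm |
|---|---|---|---|---|---|---|
| 0.15 v 0.30 | 0 v 0 | 100% | 100% | 0 v 0 | 100% | 100% |
| 0.30 v 0.60 | 0 v 0 | 81% | 87% | 0 v 0 | 98% | 99.8% |
| 0.40 v 0.80 | 0 v 1 | 20% | 9% | 0 v 0 | 84% | 91% |
| 0.50 v 1.00 | 0 v 1 | 4% | 0.2% | on the boundary | 51% | 46% |

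At k = 1 and mean 1.0, P(0) is exactly 0.5, so the median there is not stable. Higher rates do not reliably cure the problem: Poisson 0.70 v 1.40 gives 1 v 1, while 1.0 v 2.0 gives 1 v 2. If the index debridement is counted as a surgery, every median rises by 1 and the argument is the same.

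**Step 4: does the test still see it?** Power at two-sided 0.05 for 0.30 v 0.60, where both population medians are 0:

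| Distribution | Per arm | Mann-Whitney | Welch t |
|---|---|---|---|
| Poisson | 75 | 75% | 78% |
| Poisson | 150 | 96% | 97% |
| Neg. bin., k = 1 | 75 | 54% | 62% |
| Neg. bin., k = 1 | 150 | 84% | 90% |

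The p-value can therefore show a difference while the estimate reads 0 v 0.

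**Step 5: follow-up time.** SAP 1.4 sets the test of cure (TOC) 12 months after the end of antibiotics, or 18 months from the start for long-arm delayed infections treated for 6 months or more. With the durations in SAP 1.1 (8 weeks ≈ 1.8 months, 12 weeks ≈ 2.8 months), and therapy taken to start near randomisation:

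- Early infection: about 13.8 v 14.8 months (short v long), ratio 14.8/13.8 = 1.07.
- Delayed infection: about 14.8 v up to 18 months, ratio up to 18/14.8 = 1.22.

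If events are counted to TOC (the SAP does not state the window), the long arm can have more time in which to accrue them.

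**The case against.** A reader might infer that the medians will be identical, that the resource objective is bound to be answered 0 v 0, and that a real difference would go unseen. The document does not support this.

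- It gives no event rates, so it does not establish that these are low counts. The SAP lists several kinds of further surgery, and nothing shows that fewer than half of the patients will have one. With Poisson means of 0.4 v 0.8 the medians are 0 v 1.
- The tests allowed in 5.2.4 use the whole distribution. Step 4 shows that they can detect a doubling when both medians are 0.
- For surgeries, 5.2.1 already reports the proportion needing a new one, with a risk ratio and an absolute difference.
- The opening of 5.2 allows a mean where appropriate.

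The first three stand and limit the point. They do not remove it. A significant p-value beside 0 v 0 leaves the reader without a size of effect, and the test then addresses a different quantity from the one reported. Readmissions have no second summary to fall back on. The fourth carries little weight, because 5.2.4 names the median for these variables and so takes away the choice that 5.2 had left open.

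**Conclusion.** The point holds as a limited one. SAP 5.2.4 fixes a summary that can be uninformative for two counts. This happens if most patients in both arms have no event, and in some other cases where both medians fall on the same integer. Under Poisson counts the first condition means a mean below 0.693 in the arm with the higher rate; with overdispersion the limit rises to 1.0 (k = 1) or 1.5 (k = 0.5). Whether the trial falls in that range cannot be told from the SAP.

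The loss is in the effect estimate and not necessarily in the test. It is greatest for readmissions. For surgeries only the count per patient is lost. The primary non-inferiority analysis is untouched, so this is a cheap improvement to a secondary endpoint.

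**What to change.** In SAP 5.2.4, for readmissions and number of surgeries:

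1. Report the mean per patient, or the rate over follow-up, by arm.
2. Give the between-arm difference or rate ratio with a 95% CI. A bootstrap interval for the difference in means would do. A negative binomial model, or a Poisson model with robust errors, with an offset for follow-up time would also deal with any unequal time to TOC.
3. Add the proportion with at least one readmission, presented as 5.2.1 does for new surgeries.
4. State the window over which events are counted, and whether the index debridement is included.
5. Keep median and IQR as description. Medians can stay for days of antibiotics and length of stay.

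The cost is a few lines of SAP text and slightly more analysis. No new data are needed, because the counts are already to be collected.
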